6.2 Serious Adverse Event (SAE) Definition

A serious adverse event is one that at any dose (including overdose):

- Results in death
- Is life-threatening¹

- Requires inpatient hospitalization or prolongation of existing hospitalization
- Results in persistent or significant disability or incapacity²
- Is a congenital anomaly or birth defect
- Is an important medical event³

¹“Life-threatening” means that the subject was at immediate risk of death at the time of the serious adverse event; it does not refer to a serious adverse event that hypothetically might have caused death if it were more severe.

²“Persistent or significant disability or incapacity” means that there is a substantial disruption of a person’s ability to carry out normal life functions.

³Medical and scientific judgment should be exercised in deciding whether expedited reporting is appropriate in situations where none of the outcomes listed above occurred. Important medical events that may not be immediately life-threatening or result in death or hospitalization but may jeopardize the patient or may require intervention to prevent one of the other outcomes listed in the definition above should also usually be considered serious. Examples of such events include allergic bronchospasm requiring intensive treatment in an emergency room or at home, blood dyscrasias or convulsions that do not result in inpatient hospitalization, or the development of drug dependency or drug abuse. A new diagnosis of cancer during the course of a treatment should be considered as medically important.

NOTE: Pregnancies must be reported to GSK; however are not to be reported as SAEs unless they meet serious criteria.

6.3 Adverse Drug Reaction Reporting

Toxicity will be scored using CTCAE Version 4.03 for toxicity and adverse event reporting (Appendix 4). A copy of the CTCAE Version 4.03 can be downloaded from the CTEP homepage ([HTTP://CTEP.INFO.NIH.GOV](http://CTEP.INFO.NIH.GOV)). All appropriate treatment areas should have access to a copy of the CTCAE Version 4.03. All adverse clinical experiences, whether observed by the investigator or reported by the patient, must be recorded, with details about the duration and intensity of each episode, the action taken with respect to the test drug, and the patient’s outcome. The investigator must evaluate each adverse experience for its relationship to the test drug and for its seriousness.

6.3.1 Laboratory and Other Safety Assessment Abnormalities Reported as AEs and SAEs

- Any abnormal laboratory test results (hematology, clinical chemistry, or urinalysis) or other safety assessments (e.g., ECGs, radiological scans, vital signs measurements), including those that worsen from baseline, and felt to be clinically significant in the medical and scientific judgment of the investigator **are** to be recorded as AEs or SAEs.

- All events meeting liver stopping criteria must be recorded as an SAE.
- However, any clinically significant safety assessments that are associated with the underlying disease, unless judged by the investigator to be more severe than expected for the subject's condition, are **not** to be reported as AEs or SAEs.
- B cell depletion, IgG below LLN, low CD19+ count, and hypogammaglobulinemia due to treatment with ofatumumab are **not** to be reported as AEs or SAEs.
- Infusion related AEs may lead to a prolonged infusion time. Overnight stay at the hospital due to slow infusion rate is **not** to be reported as a SAE.

The investigator must appraise all abnormal laboratory results for their clinical significance. If any abnormal laboratory result is considered clinically significant, the investigator must provide details about the action taken with respect to the test drug and about the patient's outcome.

6.3.2 Disease-Related Events and/or Disease-Related Outcomes Not Qualifying as SAEs

An event which is part of the natural course of the disease under study (i.e., disease progression) does not need to be reported as an SAE. However, if the progression of the underlying disease is greater than that which would normally be expected for the subject, or if the investigator considers that there was a causal relationship between treatment with investigational product or protocol design/procedures and the disease progression, then this must be reported as an SAE.

6.4 Investigator Reporting Responsibilities

The conduct of the study will comply with all Health Canada safety reporting requirements.

CTA Annual Reports

Annual Clinical Trial Application reports, under the old Health Canada regulatory framework, have been replaced by the annual updated Investigator's Brochure. Updated Investigator's Brochures, including all safety information and global status should be submitted annually. Additional information and any changes that have been incorporated in the updated Investigator's

Brochure should be highlighted for ease of review and evaluation. If an Investigator's Brochure is updated more frequently, it should be submitted as required.

All adverse experience reports must include the patient study number, age, sex, weight, severity of reaction (mild, moderate, severe), relationship to drug (probably related, doubtful relationship, definitely not related), date and time of administration of test medications and all concomitant medications and medical treatment provided. The investigator is responsible for evaluating all adverse events to determine whether criteria for “serious” and as defined above are present. The investigator is responsible for reporting adverse events to GSK as described below.

6.4.1 Expedited reporting by investigator to GlaxoSmithKline Inc.

Serious adverse events (SAE) are defined above. The investigator must inform GSK in writing of any SAE within 24 hours of being aware of the event. The date of awareness should be noted on the report. The written report must be completed and supplied to GSK by facsimile within 24 hours/1 business day at the latest on the following working day.

All SAEs regardless of relationship to investigational product will be collected from the first dose of investigational product up to a minimum of 6 months after the last dose of investigational product or until the end of the follow-up period whichever is longer. All SAEs regardless of causality will be collected until the end of the follow-up period. SAEs are no longer required to be reported if a subject begins treatment with another therapy.

From the time a subject consents to participate in and completes the study all SAEs assessed **as related to study participation** (e.g., protocol-mandated procedures, invasive tests, or change in existing therapy) or **related to GSK concomitant medication**, will be reported promptly to GSK.

Any SAE brought to the investigator's attention after the subject has completed the study and considered by the investigator as possibly related to investigational product must be reported to GSK.

The initial report must be as complete as possible, including details of the current illness and (serious) adverse event, and an assessment of the causal relationship between the event and the investigational product(s). Information not available at the time of the initial report (e.g., an end date for the adverse event or laboratory values received after the report) must be documented on a follow-

up report. A final report to document resolution of the SAE is required. GSK numbers for SAE reporting: [contact] [contact];
email: ([name]) [contact].

In addition, the investigator or designated person will provide a brief safety update by email or telephone every 2 weeks to GSK for the duration during which study drug(s) are administered.

Pregnancy

Any pregnancy that occurs during study participation must be reported to GSK. To ensure subject safety, each pregnancy must be reported to GSK within 2 weeks of learning of its occurrence. The pregnancy must be followed up to determine outcome (including premature termination) and status of mother and child. Pregnancy complications and elective terminations for medical reasons must be reported as an AE or SAE. Spontaneous abortions must be reported as an SAE.

Any SAE occurring in association with a pregnancy, brought to the investigator's attention after the subject has completed the study and considered by the investigator as possibly related to the investigational product, must be promptly reported to GSK.

In addition, the investigator must attempt to collect pregnancy information on any female partners of male study subjects who become pregnant while the subject is enrolled in the study. Pregnancy information must be reported to GSK as described above.

6.4.2 Report of Adverse Events to the Institutional Review Board

The Principal Investigator is required to notify his/her Institutional Review Board (IRB) of a serious adverse event according to institutional policy.

6.4.3 Investigator Reporting to Health Canada

For drugs used in *clinical trials in Canada*, only adverse drug reactions (ADRs) that are *both serious and unexpected* are subject to expedited reporting to Health Canada. Expedited reporting of reactions, which are serious but expected, is not required. Expedited reporting is not required for serious events from clinical investigations that are considered unrelated to the study product, whether or not the event is expected.

During a clinical trial the sponsor is required to inform Health Canada of any serious, unexpected adverse drug reaction that has occurred inside or outside Canada. ADR report must be filed in the cases:

- where the ADR is neither fatal nor life-threatening, within 15 days after becoming aware of the information
- where it is fatal or life-threatening, immediately where possible and, in any event, within 7 days after becoming aware of the information
- within 8 days after having informed Health Canada of the ADR, submit as complete as possible, a report which includes an assessment of the importance and implication of any findings

Each ADR which is subject to expedited reporting should be reported individually in accordance with the Health Canada / ICH Guidance Document E2A: Clinical Safety Data Management: Definitions and Standards for Expedited Reporting.

Ongoing safety information respecting a drug should be conveyed to Investigator(s) and their Research Ethics Board(s). For further information refer to the Health Canada / ICH Guidance Documents E6: Guideline for Good Clinical Practice and E2A: Clinical Safety Data Management: Definitions and Standards for Expedited Reporting.

How to file an ADR report to Health Canada:

A completed ADR Expedited Reporting Summary Form should be attached to the front of the completed ADR report (suggested ADR report format: Suspect Adverse Reaction Report - CIOMS form of the Council for International Organizations of Medical Sciences (CIOMS)).

The report should be submitted by fax to the appropriate Directorate.

6.5 Adverse event updates/IND safety reports

GSK shall notify the Investigator via an IND Safety Report of the following information:

- Any AE associated with the use of drug in this study or in other studies that is both serious and unexpected.
- Any finding from tests in laboratory animals that suggests a significant risk for human subjects including reports of mutagenicity, teratogenicity, or carcinogenicity.

The Investigator shall notify his/her IRB/EC promptly of these new serious and unexpected AE(s) or significant risks to subjects.

7 Response Assessment

Baseline lesion assessments must occur within ≤ 28 days of protocol therapy initiation or as indicated in Section 2, Schedule of Study Assessments. All patients will undergo baseline imaging with CT scans of neck, chest, abdomen and pelvis.

Efficacy assessments are scheduled to occur every 4 weeks (beginning of each cycle). Response and progression will be evaluated in this study using the 2008 IWCLL criteria for response in CLL (**Appendix 5**). Radiological methodologies, techniques and/or physical examination, established at baseline, for the assessment and measurement of each identified lesion must be used for all subsequent assessments. Repeat CT scanning will be required in patients with baseline CT abnormalities in order to confirm CR only and at study discontinuation.

8 Protocol Amendments/Deviations

8.1 Protocol amendments

Any amendment to this protocol must be agreed to by the Principal Investigator and reviewed by GSK. Written verification of IRB/EC approval will be obtained before any amendment is implemented.

8.2 Protocol deviations

When an emergency occurs that requires a deviation from the protocol for a subject, a deviation will be made only for that subject. A decision will be made as soon as possible to determine whether or not the subject (for whom the deviation from protocol was effected) is to continue in the study. The subject's medical records will completely describe the deviation from the protocol and state the reasons for such deviation. In addition, the Investigator will notify the IRB/EC/Health Canada in writing of such deviation from protocol.

Non-emergency minor deviations from the protocol will be permitted with approval of the Principal Investigator.

9 Data Management

9.1 Analyses and Reporting

Data will be analyzed and reported after accrual has been completed. All subsequent data collected will be analyzed and reported in a follow-up clinical report.

9.2 Data Monitoring Committee

The Data Safety Monitoring Board (DSMB) at Princess Margaret Cancer Centre will be composed of medical and statistical independent reviewers and will meet to review the efficacy and safety data and determine a risk/benefit analysis in this subject population. The purpose of the DSMB is to advise on serious safety considerations, lack of efficacy and any other considerations within the charge to the Committee. The DSMB may request additional meetings or safety reports as deemed necessary upon discussion with GSK and its representatives. The DSMB may stop the study following review of results from any report.

9.3 Study auditing

9.3.1 Investigator responsibilities

Investigator responsibilities are set out in the ICH guideline for Good Clinical Practice (GCP) and in accordance with the rules and regulations of Health Canada's Therapeutic Products Directorate.

Investigators or a designated member of the Investigator's staff must enter study data onto CRFs or other data collection system. The Investigator will permit study-related audits by IRB/EC review, and regulatory inspection(s) (e.g., Health Canada, FDA, EMEA, TPP), providing direct access to the facilities where the study took place, to source documents, to CRFs, or other data collection system to all other study related documents.

The Investigator, or a designated member of the Investigator's staff, must be available at some time during audits to review data and resolve any queries and to allow direct access to the subject's records (e.g., medical records, office charts, hospital charts, and study related charts) for source data verification.

10 Biostatistical Analysis

10.1 Overview

This is a phase II study to investigate the efficacy of ofatumumab in combination with oral GSK2110183 in patients with relapsed or refractory CLL. The protocol will accrue 31 response evaluable patients.

10.2 Endpoints

The primary and secondary objectives will be evaluated by analysis of efficacy endpoints (response rates, response duration), progression-free and overall survival, and toxicity.

Evaluable for toxicity - All patients will be evaluable for toxicity from the time of their first dose of GSK2110183. After 6 subjects have completed cycle 1 of the Treatment Phase (on combination ofatumumab and GSK2110183), an analysis to assess safety and tolerability will be conducted.

Evaluable for response - All patients who have received at least 1 dose of GSK2110183 during the initial Lead-in Phase will be considered evaluable for response. Duration of Response (DOR) is defined, for the subset of patients with a CR or PR, as the time from first documented evidence of CR or PR until first documented disease progression or death due to any cause. If sample size permits, duration of response will be summarized descriptively using Kaplan-Meier medians and quartiles. Only the subset of patients who show a CR or PR will be included.

Evaluable for survival - All patients will be evaluable for survival. Overall survival is defined as the length of time between the date of first dose of study treatment (GSK2110183) and death due to any cause. Progression Free Survival (PFS) is defined as the length of time between the date of first dose of study treatment (GSK2110183) and the earliest date of disease progression or death due to any cause. If the patient does not have a documented date of progression or death, then PFS will be censored at the date of last adequate assessment. For a patient who is alive at the time of the statistical analysis, the patient will be considered censored at the last date of known contact.

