5.1 Overall design

This is a phase 2, open-label, single institution trial of combination IV ofatumumab and oral GSK2110183 in patients with relapsed or refractory CLL. During the initial 7 months Treatment

Phase, ofatumumab will be administered weekly for 8 doses, then once every 4 weeks cycle for an additional 4 doses (dose and schedule identical to the pivotal phase 2 trial, Wierda et al. 2010) and GSK2110183 will be given daily PO (Treatment Phase). There will be an initial 10 day lead-in with GSK2110183 alone prior to initiation of ofatumumab to allow for evaluation of changes in cell surface expression due to GSK2110183 and pharmacokinetic studies (Lead-in Phase). The official Cycle 1 Day 1 will start on the date of first dose of ofatumumab. Cycle duration = 4 weeks. Patients will be assessed for safety, disease assessment, response, and survival on day 1 of each cycle during the Treatment Phase. The safety data will be reviewed by the DSMB during their biannual meeting. Enrollment will continue while DSMB response to the review of the safety data is awaited. All patients achieving SD, PR or CR by the end of the Treatment Phase will proceed to the Maintenance Phase. Patients with PD at any time, including by the end of Treatment Phase, will be taken off study. During the Maintenance Phase, single-agent GSK2110183 will be administered daily for a maximum of 11 months (11 cycles). Maximum duration on any study drug is 18 months (18 cycles). During the Follow-up Phase, patients will be assessed for safety, disease assessment, response, and survival every 3 months through month 36 (year 3), or until subsequent CLL therapy or death, whichever comes first. Key indications for study withdrawal are progressive disease, intolerable toxicity or completion of therapy.

G - GSK2110183 125mg OD continuously

O – Ofatumumab: The dosage regimen is 300mg Ofatumumab for the first infusion and 2000 mg Ofatumumab for all subsequent infusions. The infusion schedule is 8 consecutive weekly infusions, followed 4 weeks later by 4 consecutive monthly (i.e. every 4 weeks) infusions.

* PK sampling on Day 10 of lead-in phase and with 8th weekly dose of ofatumumab (see Appendix 6)

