10.4 Safety evaluation

Data from all subjects who receive any protocol therapy will be included in the safety analyses. Subjects who entered the study and did not receive any protocol therapy and had this confirmed, will not be evaluated for safety. Severity of adverse events will be graded by NCI Common Terminology criteria version 4.03. SAEs will be reported at a minimum of up to 6 months after the last dose or to the end of the follow-up period whichever is longer. If a subject starts other therapy, then SAEs will

no longer be required to be reported. Note: Causality must be assessed for each study drug separately. SAE forms used must allow for attribution for each study drug to be documented separately. A formal review of safety data after the first 6 patients have completed cycle 1 of the Treatment Phase will be performed before continuing accrual.

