10.5 Patient Accrual and Study Duration

Accrual for this study is expected to be about 2 patients per month. Thus, patient accrual is expected to be complete within 18-24 months. Additional time will be required to allow the response data to mature.

All patients registered in the study will be accounted for. The number of patients who die or withdraw before treatment begins will be specified. The distribution of follow-up times will be described and the number of patients lost to follow-up will be given.

11 Regulatory Considerations

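### The six-patient safety review is timed by Cycle 1 completers, so it comes later the more patients stop early for toxicity

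*Combined protocol and SAP*

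**What the plan says.** Two places describe the review, and both count completers.

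- Section 10.2: "After 6 subjects have completed cycle 1 of the Treatment Phase (on combination ofatumumab and GSK2110183"), a safety and tolerability analysis is carried out.
- Section 10.4: a formal safety review "after the first 6 patients have completed cycle 1 of the Treatment Phase will be performed before continuing accrual".

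Neither place counts a patient who stops before the end of Cycle 1, defines completion, caps the number dosed before the review, or sets a toxicity-based trigger. Section 10.2 does make the safety population wider than the trigger: "All patients will be evaluable for toxicity from the time of their first dose of GSK2110183". Sections 10.3.1 and 10.4 agree that anyone who has received therapy is in the safety data.

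The time a patient needs to complete comes from section 5.1: "There will be an initial 10 day lead-in with GSK2110183 alone prior to initiation of ofatumumab", then one cycle, with "Cycle duration = 4 weeks". Section 10.5 gives the pace: "Accrual for this study is expected to be about 2 patients per month".

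The synopsis and section 5.1 describe twice-yearly DSMB reviews and say that enrolment carries on while the DSMB's answer is pending. Section 10.4 instead places the six-patient review ahead of further accrual.

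**The concern.** The review is the planned early check on a combination for which the plan cites no earlier clinical data; section 3.2.1 only anticipates good tolerability. GSK2110183 starts at the dose that section 5.1.2 calls the maximal tolerated dose as a single agent.

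The plan has several routes out before Cycle 1 ends: unresolved or recurrent severe infusion reactions (5.4.3), removal when ofatumumab is discontinued for infusional events (5.5.3.1), grade 4 rash (5.5.4), the liver chemistry criteria (5.7.1.1) and the QTc criteria (5.7.1.2). A patient who takes one of these routes leaves the count of six unchanged, and the review waits for a replacement. The wait therefore grows with the problem the review is there to find, and more patients may be dosed meanwhile.

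**Working it through.** **Plan's own figure.** The plan gives no operating characteristic for this review, so there is none to reproduce. The efficacy rule in 10.3.2 (19 or more responses of 31, 0.470 against 0.670) does reproduce, with exact error rates of 0.0786 and 0.1915 against the stated 0.079 and 0.192. It is unaffected by this point.

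**Inputs from the documents.** Six completers (10.2, 10.4); 10 + 28 = 38 days from first dose to the end of Cycle 1 (5.1), which is 38/30.4375 = 1.25 months; accrual of 2 per month (10.5).

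**Assumed input.** d is the chance that a dosed patient stops for toxicity before the end of Cycle 1. The documents give no value, so a range is shown. Other early exits are ignored here.

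**Formulas.**

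1. Mean number dosed to obtain six completers (negative binomial): 6/(1 − d).
2. Mean number of early stoppers dosed ahead of the sixth completer: 6/(1 − d) − 6 = 6d/(1 − d).
3. Mean months from the first patient's first dose to the present trigger: [6/(1 − d) − 1]/2 + 1.25.
4. If early toxicity stops counted, the trigger would fall, on average, no later than the point at which the sixth dosed patient reaches day 38: (6 − 1)/2 + 1.25 = 3.75 months.
5. Mean delay is therefore at least [6d/(1 − d)]/2 months. It is a lower bound because a patient who stops early is counted before day 38.

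| d (assumed) | Mean dosed for 6 completers | Early stoppers ahead of the 6th completer | Months to present trigger | Delay, at least (months) | Dosed by trigger if accrual never pauses |
|---|---|---|---|---|---|
| 0 | 6.0 | 0 | 3.75 | 0 | 8.5 |
| 0.20 | 7.5 | 1.5 | 4.5 | 0.75 | 10.0 |
| 0.33 | 9.0 | 3.0 | 5.2 | 1.5 | 11.5 |
| 0.50 | 12.0 | 6.0 | 6.75 | 3.0 | 14.5 |

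The last column is 1 + 2 × (months to trigger). Example at d = 0.20: 6/0.80 = 7.5; (7.5 − 1)/2 + 1.25 = 4.5; 4.5 − 3.75 = 0.75; 1 + 2 × 4.5 = 10.0.

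**Sensitivity to accrual.** Section 10.5 also expects 18 to 24 months for 31 patients. Over 24 months that is 31/24 = 1.3 per month. The delay is then 1.5/1.3 = 1.2 months at d = 0.20 and 6.0/1.3 = 4.6 months at d = 0.50.

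**Wording of 10.4.** Read as the first six patients enrolled, the condition needs all six to complete. That has probability (1 − d)^6: 0.26 at d = 0.20 and 0.016 at d = 0.50.

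**The case against.** The strongest reply is that the trigger sets a date, not an analysis set. That stands. A reader might infer that the review would examine only a tolerant subset, but 10.2, 10.3.1 and 10.4 put every dosed patient in the safety data, so early stoppers are seen once the review takes place.

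A reader might also infer that this is the only early look. It is not. SAEs go to GSK within 24 hours and safety updates go to GSK every two weeks (6.4.1). The DSMB may call extra meetings or reports and may stop the study (9.2). None of these is tied to early discontinuation, so they soften the delay without removing it. If twice-yearly means every six months, the mean time to the trigger passes that interval only at the top of the assumed range (6.75 months at d = 0.50).

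d is not the toxicity rate. Within a cycle, doses can be held while the 28-day schedule runs on (5.5.3.1, 5.5.3.2), GSK2110183 has four reduction levels (5.5.1), and a patient who cannot tolerate the lowest level may stay on ofatumumab alone. Many toxicities would therefore not prevent completion, and 0.33 and 0.50 have no anchor in the documents. This stands as a limit on size.

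It is tempting to count as uncounted stoppers everyone dosed by the trigger date who will eventually stop, d × the last column: 2.0, 3.8 and 7.2. Those figures include patients still inside their own 38 days, who have not held up anything. The relevant means are 1.5, 3.0 and 6.0.

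Finally, a reader might infer from 10.4 that one early stop makes the review impossible. The text can be read that way, but it can equally mean the first six to complete. On the stricter reading accrual would stall rather than run on. This shows unclear wording, not extra exposure.

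**Conclusion.** The point holds as a timing defect. Both statements of the trigger count completers, so the review moves later as early stopping for toxicity rises. The delay is under a month at d = 0.20 and 2 patients per month, and about three months at d = 0.50. These are lower bounds on the mean, and they rest on an assumed d, steady accrual, 38 days to completion and no other early exits. The number exposed by the trigger date also depends on whether accrual pauses, which the documents leave contradictory. The content of the review is not biased, and other oversight partly covers the gap. Severity is minor to moderate: the effect is modest when few stop early and largest when the combination is poorly tolerated.

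**What to change.** In both 10.2 and 10.4, state that the review takes place when six dosed patients have each either completed Cycle 1 of the Treatment Phase or stopped protocol therapy earlier because of toxicity. Patients who stop earlier for other reasons, such as withdrawn consent, do not count towards the six. Add that the review covers all patients dosed by the cut-off, shows lead-in stops separately from stops on the combination, and lists the reason for each early stop. Define completion for a patient whose dosing was interrupted.

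In the same edit, reconcile 10.4, which puts the review before further accrual, with the synopsis and 5.1, which say enrolment continues while the DSMB response is awaited.

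The cost is one or two sentences in two places; no dose or sample-size figure changes. The downside is that some counted patients will have little combination exposure, and those who stop in the lead-in will have had no ofatumumab at all. That is why lead-in stops are shown separately.
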